### **3. STUDY DESIGN**

This is a Phase 3, randomized, double-blind, placebo-controlled study to evaluate the efficacy, safety, and tolerability of crinecerfont versus placebo administered bid with breakfast and the evening meal (doses separated by approximately 12 hours) for 24 weeks in approximately 165 adult subjects with classic congenital adrenal hyperplasia (CAH) due to 21-hydroxylase deficiency. Eligible subjects will be randomly assigned in a 2:1 ratio (active:placebo) to 2 treatment groups, crinecerfont 100 mg bid or placebo. After the 24-week randomized treatment period, there will be a 6-month, open-label treatment period, during which all subjects will receive crinecerfont 100 mg bid. At Month 12, subjects who have not reduced their glucocorticoid dose to  $\leq 11 \text{ mg/m}^2/\text{day}$  will be re-randomized (2:1) to receive 100 mg every morning (qAM) and 200 mg every evening (qPM) or to continue 100 mg bid, in a blinded fashion. Subjects who have reduced their glucocorticoid dose to  $\leq 11 \text{ mg/m}^2/\text{day}$  will continue to receive 100 mg bid in an open-label fashion. At Month 18, subjects will review applicable portions of the informed consent form and confirm whether they will participate in the optional open-label extension (OLE) treatment period for continued access to crinecerfont. Starting at Month 18, all subjects who are continuing in the OLE will initially receive crinecerfont 100 mg bid. If the subject has inadequate disease control despite receiving glucocorticoid treatment at their target dose (in the opinion of the investigator), the crinecerfont dose may be increased to 100 mg qAM and 200 mg qPM. After the Month 24 visit, an alternative dosing regimen of once daily 200 mg qPM can be considered per the investigator. Subjects will remain in the OLE until crinecerfont becomes commercially available, the Sponsor elects to discontinue development of crinecerfont for CAH, the Sponsor elects to discontinue the study, or the subject meets one of the study withdrawal criteria. A final study visit will be conducted approximately 4 weeks after the last dose of study drug.

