#### **3.1. Randomization**

Approximately 165 eligible subjects will be randomized 2:1 to either crinecerfont or placebo on Day 1 using an interactive response technology (IRT). Randomization will be stratified by total daily glucocorticoid regimen on Day 1 ( $<20 \text{ mg/m}^2/\text{day}$  or  $\geq 20 \text{ mg/m}^2/\text{day}$  in hydrocortisone dose equivalents adjusted for BSA), glucocorticoid type (hydrocortisone alone; prednisone, prednisolone, methylprednisolone, with or without hydrocortisone; dexamethasone, with or without another glucocorticoid), and sex.

Subjects with glucocorticoid dose  $>11 \text{ mg/m}^2/\text{day}$  (hydrocortisone dose equivalents) at Month 12 will be re-randomized 2:1 to a modified regimen of 100 mg qAM and 200 mg qPM or to continue crinecerfont at 100 mg bid. Month 12 randomization will be stratified by the original treatment assignment (crinecerfont versus placebo) and by Month 12 glucocorticoid dose ( $>14 \text{ mg/m}^2/\text{day}$  versus  $\leq 14 \text{ mg/m}^2/\text{day}$ ). Subjects who discontinue study drug prior to Month 12 are ineligible for re-randomization.

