### **3.3. Sample Size Considerations**

The protocol-specified sample size of 165 subjects (110 in the crinecerfont treatment group and 55 in the placebo group) is based on a power calculation for the primary endpoint and considerations for the size of the safety database. Based on a 2-sample t-test, an effect size of 0.75 with a sample size of at least 90 subjects (60 in the crinecerfont treatment group and 30 in the placebo treatment group) will have greater than 90% power to detect a treatment difference at a 0.05 level of significance. With the full sample size of 165 subjects, there is greater than 90% power to detect an effect size as small as 0.55. Sample size and power estimates were obtained from nQuery® Advisor Version 8.

A single planned interim analysis detailed in Section 5.1, with a futility analysis and an unblinded sample size re-estimation, will be performed when approximately the first 76 randomized subjects (approximately 46% of the planned number of enrolled subjects) have had the opportunity to be assessed for the primary endpoint. The unblinded sample size re-estimation may result in an increase of the overall sample size to a maximum of 210 subjects.

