### **6.3.2. Baseline Definition for Analyses of OL Period Data**

Two baselines will be defined for analyses of data from the OL period. For all efficacy summaries in the OL period, the Week 24 assessments collected prior to the first dose of study drug in the OL period will serve as one of the baseline values for assessments through Month 12 of the study. This baseline will be referred to as the “OL baseline” throughout this document. Unless otherwise noted, all efficacy summaries will be repeated using the study baseline (as defined in Section 6.3.1). For both the OL baseline and study baseline, if the respective Week 24 or Day 1 value is not available, then the last measurement collected prior to study drug in each period will serve as baseline. Specifically, for the OL period, if the Week 24 value is not available, then the last measurement collected prior to study drug in the OL period will serve as baseline as long as the last non-missing measurement is not the study baseline value. For assessments that are performed every 6 months, if the Week 24 assessment is not available then the OL baseline and postbaseline values will not be included in the summary.

Body composition assessments obtained within 2 weeks after Week 24 may serve as the OL baseline if needed. Bone mineral density and testicular ultrasound assessments obtained within 1 month after Week 24 may serve as the OL baseline value if needed, as these parameters are not expected to change to a degree that could be clinically detected over this time frame.

Note that for hormone parameters that are collected both pre- and post-GC dose, OL baselines will be defined as the last pre- or post-GC dose value available prior to study drug dosing at Week 24 for all pre- and post-GC postbaseline values (after Week 24), respectively, where a change from OL baseline calculation is necessary, unless otherwise specified.

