## 11. SAFETY

The safety objective of the study is to characterize the safety and tolerability profile of crinecerfont as measured by TEAEs (including SAEs), clinical laboratory tests, vital signs, ECG, and neuropsychiatric assessments. All outputs for safety endpoints during the DB period will be based on the DB Period Safety Analysis Set. Safety data will be summarized descriptively by treatment group. All outputs for safety endpoints during the OL period will be based on the OL Period Safety Analysis Set and will be summarized descriptively by treatment group. Safety data will not be subject to any imputation and will be summarized on an observed case basis. No formal hypothesis-testing analysis of safety data will be performed. Unless otherwise noted, the below summaries will be produced for both the DB period and the OL period safety data separately and will follow the treatment-period specific treatment group and baseline definitions (as described in Section 6). All by-visit safety tables will also include a safety follow-up visit summary (as defined in [Table 5](#)) and subject data collected after the safety follow-up visit will not be summarized.

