## 11.5. Electrocardiogram

Descriptive statistics for the observed values and changes from baseline will be presented for each of the ECG parameters (heart rate, PR interval, QRS duration, QT interval, QTcF) by visit and treatment group.

Frequency tables (number and percentage of subjects) will be presented for the investigator overall categorical assessment (ie, Normal, Abnormal not Clinically Significant, or Abnormal Clinically Significant) by visit and treatment group.

Two additional categorical summaries (frequency tables displaying number and percentage of subjects) will be presented for the QTcF interval by treatment group. For the first summary, the observed QTcF values at each visit will be classified as follows:

- Greater than 450 msec
- Greater than 480 msec
- Greater than 500 msec

For the second categorical summary, the changes from baseline to each subsequent visit will be classified as follows:

- Increase greater than 30 msec
- Increase greater than 60 msec

The same categorical summaries will be presented in frequency tables for values at any postbaseline visit (including unscheduled and early termination visits) meeting the aforementioned criteria.

The above ECG summaries will be produced for the DB period and the OL period separately.

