## **11.7. Brief Psychiatric Rating Scale (BPRS)**

The Brief Psychiatric Rating Scale (BPRS) is a clinician-rated tool designed to assess the severity of psychopathology in subjects with schizophrenia and other psychotic disorders. The BPRS includes 18 items that address somatic concern, anxiety, emotional withdrawal, conceptual disorganization, guilt feelings, tension, mannerisms and posturing, grandiosity, depressive mood, hostility, suspiciousness, hallucinatory behaviors, motor retardation, uncooperativeness, unusual thought content, blunted affect, excitement, and disorientation. The severity of each of the 18 items of the BPRS is rated on a scale of 1 (not present) to 7 (extremely severe) (total score range: 18 to 126). Higher scores represent greater symptom severity. Items that are not scored are left blank (i.e., not score as “0”). Rather than using the EDC total score value, the total score for BPRS will be re-calculated as the sum of the ratings for each of the 18 items. Missing items will be imputed based on the average score of the other items at that assessment; however, if >50% of the items are missing for that subject/visit, then the total score will be set to missing.

BPRS total score observed and change from baseline values will be summarized with descriptive statistics by visit and treatment group. This summary will be produced for the DB period and the OL period separately. The study baseline will be used for the DB period summaries while the OL baseline will be used for the OL period summaries.

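### For subjects on crinecerfont since Day 1, open-label changes in BPRS, and on the natural reading in ECG, vital signs and continuous laboratory values, have no stated repeat from the pre-drug baseline

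*SAP*

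**What the plan says.** SAP Section 11 has safety outputs produced for the DB and OL periods separately. Unless otherwise noted, they "will follow the treatment-period specific treatment group and baseline definitions (as described in Section 6".

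Section 6.3.1 makes the Day 1 value the baseline for assessments through Week 24. Section 6.3.2 names two baselines for OL data. It introduces the Week 24 value, called the OL baseline, in a sentence about efficacy summaries, and then adds: "Unless otherwise noted, all efficacy summaries will be repeated using the study baseline (as defined in Section 6.3.1". It has no matching sentence for safety.

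The safety subsections differ:

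- **BPRS (11.7)** is explicit: "The study baseline will be used for the DB period summaries while the OL baseline will be used for the OL period summaries".
- **ECG (11.5)** plans mean changes and counts of QTcF increases above 30 and 60 msec: "For the second categorical summary, the changes from baseline to each subsequent visit will be classified as follows". The same counts are made for any postbaseline visit, and all are produced by period. The text does not say which baseline applies in the OL period.
- **Vital signs (11.4)** and **continuous laboratory values (11.3)** plan changes from baseline by period, again without naming it.
- **Laboratory shift tables (11.3)** for the OL period run both from study baseline and from OL baseline to Month 12, for 13 listed analytes.

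On treatment, SAP Section 3 says that after Week 24 "there will be a 6-month, open-label treatment period, during which all subjects will receive crinecerfont 100 mg bid". SAP 6.1 displays OL data as placebo/crinecerfont, crinecerfont/crinecerfont and all subjects combined.

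**The concern.** Week 24 is the last pre-drug value for placebo/crinecerfont subjects. For crinecerfont/crinecerfont subjects it is a value after 24 weeks on 100 mg bid. A change from Week 24 in that group is a difference between two on-drug values. It answers whether anything moved further, not how far the subject now is from the untreated state.

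The second question is the usual purpose of the QTcF categories above 30 and 60 msec. QTcF matters in this trial: it is an exclusion criterion (Protocol 8.2) and a mandatory drug-stopping criterion (Protocol 9.10.1). DB tables stop at Week 24 and OL tables restart there, so a slow cumulative rise is split into two parts that are never added. SAP 11.1, by contrast, counts exposure cumulatively across both periods.

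The combined OL column also mixes a pre-drug to on-drug change in one group with an on-drug difference in the other.

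**Working it through.** **1. Share affected.** SAP 3.1: "Approximately 165 eligible subjects will be randomized 2:1 to either crinecerfont or placebo on Day 1". SAP 3.3: "The protocol-specified sample size of 165 subjects (110 in the crinecerfont treatment group and 55 in the placebo group". So 110/165 = 0.667, or two-thirds, and 55/165 = one-third. These are planned randomized numbers. The OL Period Safety Analysis Set requires an OL dose, and its split will depend on discontinuations that the documents do not give.

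**2. Which baseline applies in the OL period.**

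| Output | Week 24 baseline | Day 1 repeat |
|---|---|---|
| Efficacy summaries (6.3.2) | stated | stated |
| Laboratory shifts, 13 analytes (11.3) | stated | stated |
| BPRS (11.7) | stated | none |
| ECG change, including QTcF >30/>60 msec (11.5) | inferred from Section 11 | none stated |
| Vital signs (11.4) | inferred | none stated |
| Continuous laboratory change (11.3) | inferred | none stated |

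Sodium, potassium and the coagulation tests are not among the 13 analytes.

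**3. A constructed subject** in the crinecerfont/crinecerfont group, with QTcF 380 msec on Day 1, 420 at Week 24 and 445 at Month 12:

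- DB table: 420 − 380 = +40, counted as >30 msec.
- OL table from Week 24: 445 − 420 = +25, counted in neither category.
- Day 1 to Month 12: 445 − 380 = +65, which exceeds 60 msec but is in no planned table.
- Absolute categories (>450, >480, >500 msec): 445 is below all three.

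The subject is flagged once, in the DB table at >30 msec, and never at >60 msec. The scheduled OL ECGs at which this could happen are Months 8 and 12 (Protocol 9.6.7).

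**4. Means under a steady effect.** Let d be a shift reached by Week 24 and constant afterwards. The mean OL change from Week 24 is 0 in crinecerfont/crinecerfont and d in placebo/crinecerfont. The combined column shows d × 55/165 = d/3. For d = 5, 10 and 20 msec that is 1.7, 3.3 and 6.7 msec.

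**5. Flag rates, illustration only.** With a normally distributed within-subject change of SD s, P(change > 30) = 1 − Φ((30 − d)/s) from Day 1, and 1 − Φ(30/s) from Week 24. The documents give neither d nor s; all values here are assumed.

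| d (msec) | s (msec) | From Day 1 | From Week 24 |
|---|---|---|---|
| 5 | 15 | 4.8% | 2.3% |
| 10 | 10 | 2.3% | 0.1% |
| 10 | 15 | 9.1% | 2.3% |
| 10 | 20 | 15.9% | 6.7% |
| 20 | 15 | 25.2% | 2.3% |

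Because d is already present at Week 24 in this model, the Day 1 rates would also appear in the DB Week 24 table beside placebo. The gap describes how differently the OL table reads under the two baselines. It does not measure signal missing from the report.

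**The case against.** Three stronger readings are tempting, and the documents do not support them.

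**That a sustained drug effect is removed from the safety analysis.** An effect present by Week 24 is shown in the DB tables as change from Day 1 with a concurrent placebo arm. Observed values by visit are planned for ECG, vital signs, laboratory values and BPRS. The absolute QTcF categories need no baseline. The placebo/crinecerfont column gives a true pre-drug to on-drug change. This objection stands. It limits the loss to cumulative change after Week 24.

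**That the SAP fixes Week 24 for every safety domain.** It does so only for BPRS. Section 6.3.2 words its rule for efficacy. Section 11.3 uses the bare word baseline for Day 1 when it contrasts this with OL baseline, and the parallel introduction to Section 12 names the OL baseline outright where Section 11 does not. A programmer could therefore read 11.4 and 11.5 as meaning Day 1. Against that, Section 11 asks for period-specific definitions and 6.3.1 limits the Day 1 baseline to assessments through Week 24, so Week 24 is the more natural reading. What stands is that the choice is inferred and needs stating.

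**That laboratory values have no comparison with Day 1.** The shift tables supply one for 13 analytes, including liver enzymes, bilirubin and neutrophils, the laboratory finding that Protocol 9.6.1 discusses specifically. Only continuous changes, and analytes outside that list, lack it.

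It is also fair to say that OL safety is descriptive and untested, that OL ECGs and BPRS are few, and that Protocol 5.2 and 5.3 report no clinically relevant ECG findings in earlier studies. Nothing in the documents supports a QTcF effect of 10 to 20 msec.

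**Conclusion.** The point holds in a limited form. As written, no planned OL table shows change from the pre-drug value for crinecerfont/crinecerfont subjects in BPRS. On the natural reading the same is true of ECG change (including the >30 and >60 msec categories), vital signs and continuous laboratory values. This concerns two-thirds of subjects as planned, and the group with the longest exposure.

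What can be missed is a cumulative rise that first crosses a threshold in the OL period, as in the +40 then +65 msec example. Effects established by Week 24 are not lost. The percentages in the working are conditional on assumed d and SD and should not be cited as an estimate of missed events. For ECG, vital signs and continuous laboratory values the conclusion rests on reading the Section 11 cross-reference as Week 24. If Day 1 was meant, the text still has to say so. This is an inexpensive improvement to reporting and leaves the DB safety comparison untouched.

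**What to change.** In SAP 6.3.2 and Section 11:

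- State which baseline applies to OL-period safety changes in each domain.
- For crinecerfont/crinecerfont subjects, repeat the OL summaries of ECG change, vital signs, continuous laboratory values and BPRS from the Day 1 study baseline. Include the QTcF >30 and >60 msec counts, both by visit and at any postbaseline visit.
- Keep Week 24 as the pre-drug baseline for placebo/crinecerfont subjects.
- Show results by OL treatment group. If a combined column is kept, add a footnote saying that it pools about 12 months of change on drug with about 6.

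The Week 24-based tables for crinecerfont/crinecerfont can stay as a display of further change. The cost is SAP wording, one derived baseline flag and a few more descriptive tables. No new data are needed. The one drawback is the mixed exposure length in the combined column, which display by group avoids.

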### 11.1. Study Drug Dosing and Compliance

The duration of exposure to crinecerfont will be calculated as: (last dose date – first dose date +1) regardless of when the exposure to crinecerfont began and ended (i.e., duration of exposure to crinecerfont will be an overall measure of exposure over the DB and OL periods and will not be presented separately for the DB and OL periods).

Duration of exposure will be summarized with descriptive statistics. The number and percentage of subjects with the following exposure categories will also be presented:

- > 0 to < 4 weeks
- $\geq$  4 weeks to < 24 weeks
- $\geq$  24 weeks to < 9 months
- $\geq$  9 months to < 12 months
- $\geq$  12 months

At each visit where study drug is dispensed, the site will enter the kit number(s) dispensed and returned as well as the total number of capsules dispensed and returned for the kits combined. The subject's compliance will be calculated at each visit (when kits are returned) as the total number of capsules dispensed – total capsules returned divided by the expected number of capsules taken by the subject during the visit interval. The number and percentage of subjects in each treatment group who are dosing compliant (defined as  $>120\%$ ,  $\geq 80\%$  to  $\leq 120\%$ , and  $<80\%$ ) will be presented for each postbaseline visit where study drug is returned. Compliance will be summarized separately for the DB and OL periods.

### 11.2. Adverse Events

A treatment-emergent adverse event (TEAE) is an AE not present prior to the initiation of study drug dosing, or is an already present event that worsens either in intensity or frequency following the initiation of study drug dosing with an onset on or before the last dose of study drug + 28 days (to account for the study drug washout period).

TEAEs will be further defined for the two treatment periods. For the DB period, Investigators will be asked to respond “Yes” or “No” on the eCRF as to whether the AE started after the subject took the first dose of study drug. An AE with a response of “Yes” and that occurs on or before the last dose of study drug in the DB period will be classified as a TEAE for the DB period. If the subject’s last dose on study occurs in the DB period, then any AE occurring prior to the last dose of study drug in the DB period + 28 days will be considered a TEAE. If the investigator’s response is missing, then the treatment emergent status will be derived based on the AE onset date relative to the date of the subject’s first dose of study drug in the DB period or first dose of study drug in the OL period. If the AE onset date is unknown, it will be assumed that the AE is a TEAE and will be reported in the DB period TEAE summaries.

For the OL period, TEAEs will be defined as AEs starting after the first dose of study drug in the OL period and prior to the last dose of study drug in the OL period. If the subject’s last dose on study occurs in the OL period, then any AE occurring prior to the last dose of study drug in the OL period + 28 days will be considered a TEAE.

Adverse events with an onset date after the last dose of study drug + 28 days will not be considered treatment emergent (non-TEAEs).

The following TEAE summaries will be produced for the DB period (Day 1 up to Week 24) and for the 6-month OL period (Week 24 to Month 12) separately:

TEAEs categorized by MedDRA system organ class (SOC) and/or preferred term (PT) will be summarized in frequency tables. The frequency tables will include the number and percentage of unique subjects experiencing each event one or more times by treatment group.

Two similar frequency tables will be generated for TEAEs—one including both SOC and PT (sorted in alphabetical order), and one including PT only, with PTs sorted in order of decreasing frequency of subjects reporting the PT in the DB crinecerfont treatment group. Non-TEAEs will be summarized by SOC and PT only.

An overall summary table will be provided that summarizes the number and percentage of unique subjects with any TEAE, any SAE, any TEAE leading to study drug discontinuation, any TEAE leading to study discontinuation, and any TEAE resulting in death. The summary table will also include the frequency distribution of the maximum TEAE intensity (mild, moderate, severe) reported for each subject.

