Transient elevations in androstenedione in the absence of symptoms are not a reason for stopping the glucocorticoid dose reduction. It is expected that subjects may experience symptoms such as fatigue, nausea, abdominal discomfort, joint aches, etc, especially as doses are decreased towards the physiologic range. Subjects should be advised of this possibility and should contact the investigator if the symptoms become severe or prolonged.

A glucocorticoid dose of 8 mg/m²/day (hydrocortisone equivalents) provides systemic cortisol at approximately 70th percentile of normal glucocorticoid production rate ([Linder et al., 1990](#)). The use of this replacement dosage has not been associated with glucocorticoid insufficiency in prior studies of patients with classic CAH ([Merke et al., 2000](#)).

Based on the subject's starting and target glucocorticoid doses, the investigator will have a detailed schedule for the glucocorticoid dose reduction that will occur between Weeks 4 and 12. Details of the subject's baseline glucocorticoid regimen and dose reduction schedule will be submitted for Sponsor review prior to randomization. Specific standardized schedules for commonly used glucocorticoid dosing regimens will be provided in the study reference manual. Guidance will be provided for the glucocorticoid dose reduction schedule if a standardized schedule is not available for a subject's baseline glucocorticoid regimen. This schedule may include specific details (for each of the dose reduction steps) such as the total daily dose of each glucocorticoid (if more than 1 type of glucocorticoid taken), the breakdown of doses over the course of the day (eg, morning, afternoon, evening), and the exact number of pills at each dosage strength to be taken at each time during the day, including whether splitting of tablets is required or liquid formulations are used. If splitting of tablets is needed during glucocorticoid dose adjustments, using a smaller dosage strength (if available) in order to avoid quartering of tablets is recommended. In addition, it is recommended that the same formulation (liquid or tablet) of a given glucocorticoid be used during the glucocorticoid dose reduction as used at baseline.

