### **11.2.1. Adverse Events Resulting in Discontinuation from Study Drug**

The number and percentage of subjects with a TEAE resulting in study drug discontinuation will be presented by PT within SOC (presented in the same method as the analogous primary TEAE table) by treatment group. More than one AE can contribute to study drug discontinuation per subject. The first line of each table will display the number and percentage of subjects with at least one TEAE leading to study drug discontinuation. This summary will be produced for the DB period and OL period separately.

A listing of TEAEs resulting in premature study drug discontinuation will be provided, which will include subject ID, treatment period, treatment group, study day of the discontinuation, and other relevant information from the AE eCRF.

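### SAP 11.2's period rules classify AEs by start only, so an AE that begins in the double-blind period and worsens on open-label crinecerfont is not counted in the open-label TEAE tables

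*SAP*

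**What the plan says.** SAP 11.2 opens with a general definition of a TEAE. Besides new events it includes one that "is an already present event that worsens either in intensity or frequency following the initiation of study drug dosing".

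It then defines TEAEs further for each period, and those rules feed separate DB and OL tables.

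- **DB period.** The eCRF asks "whether the AE started after the subject took the first dose of study drug". The answer is then used to classify the event: "An AE with a response of “Yes” and that occurs on or before the last dose of study drug in the DB period" is a DB-period TEAE. If the answer is missing, "the treatment emergent status will be derived based on the AE onset date".
- **OL period.** "TEAEs will be defined as AEs starting after the first dose of study drug in the OL period" and before the last OL dose. A further sentence covers subjects whose last dose on study falls in the OL period. It treats as a TEAE any AE that occurs earlier than 28 days after that dose, and it gives no lower date limit.

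On discontinuations, SAP 11.2.1 says: "The number and percentage of subjects with a TEAE resulting in study drug discontinuation will be presented by PT within SOC". The table is produced once per period, with no rule for assigning an event that starts in one period and stops drug in the next.

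Protocol 11.2 gives each AE its own eCRF entry with onset date, resolution date and intensity. It does not tell sites to open a new entry when intensity rises.

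**The concern.** The general definition and the period rules do not match. The first has a worsening clause. The second, which decide what goes into each table, do not.

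This matters most for subjects randomized to placebo. Their first crinecerfont dose is on the evening of the Week 24 visit, so the OL period is where their on-drug safety is read. Those still above 11 mg/m²/day at Month 7 then face another glucocorticoid reduction at Months 7 to 9. Protocol 9.3.1 foresees symptoms as doses fall: "It is expected that subjects may experience symptoms such as fatigue, nausea, abdominal discomfort, joint aches, etc". A symptom that began during the first reduction, persisted past Week 24 and intensified on open-label drug would be counted only in the placebo column of the DB tables. If a site simply raises the intensity on the existing record, the DB summary of maximum intensity could also show as placebo severity something that arose on crinecerfont. The documents do not say how sites record such a change.

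For subjects already on crinecerfont in the DB period the drug attribution is right and only the period is wrong.

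**Working it through.** No stated figure is to be reproduced here. The check applies the SAP 11.2 rules to test events.

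**Assumed dates.** First dose Day 1. Last DB dose and first OL dose Day 168, the Week 24 target day in SAP Table 4.

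**Rules as coded.**
- General: onset on or after Day 1, or worsening on or after Day 1.
- DB: onset from Day 1 to Day 168.
- OL: onset after Day 168 and before the last OL dose. If the last dose on study is in the OL period, the upper limit moves to last dose + 28 days.

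| Event | General definition | DB TEAE | OL TEAE |
|---|---|---|---|
| A. Onset Day 100 on placebo, worsens Day 200, subject continues | yes | yes | **no** |
| B. As A, but OL drug stopped on Day 205 | yes | yes | **no** if the 28-day sentence only extends the window; yes if read literally |
| C. Onset Day -5, worsens Day 200 | yes | no | no |
| D. Onset Day -5, worsens Day 60 | yes | no | no |
| E. New onset Day 200 | yes | no | yes |

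**Event A** is the clear failure. The general definition recognizes worsening, yet no rule brings it into the period in which it happened.

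**Event B** is ambiguous. The 28-day sentence speaks of AEs that occur, not AEs that start. With no lower limit, a literal reading admits the Day 100 event (100 < 205 + 28 = 233). It would equally admit every earlier AE of that subject, so it is more naturally an extension of the upper limit. The text does not settle it.

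**Events C and D** look like losses under the onset rules, but other text largely covers them. Protocol 11.1 makes worsening of a condition present at study start an AE in its own right. Recorded that way, the event has its own entry with an onset after first dose and passes the period rule. That clause does not reach an AE that first appeared during the DB period, so it does not help A or B.

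**Size.** The documents give no rate of ongoing AEs at Week 24 or of later worsening. For placebo-onset events, the subjects at risk are at most the 55 planned for placebo (70 if the sample size is raised to 210, since 210/3 = 70). As an illustration on assumed rates only, let 20% to 40% of 55 enter the OL period with an ongoing AE and 5% to 15% of those worsen:

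- low: 55 × 0.20 × 0.05 = 0.55 subjects
- high: 55 × 0.40 × 0.15 = 3.3 subjects

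**The case against.** A reader might go further and infer that these events vanish from reporting, that harms severe enough to stop open-label crinecerfont are hidden, or that they are definitely tabulated against placebo. The documents do not support that.

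- An AE that began on placebo is not dropped. It stays in the DB table, and counting its onset there is correct. What is missing is the second count, for the worsening.
- Pre-dose AEs do not disappear. SAP 11.2 summarizes non-TEAEs by SOC and PT. It attaches that label explicitly only to late-onset AEs, but pre-dose AEs fall there on a natural reading.
- A stop is visible. The OL disposition table in SAP 7.1 gives reasons for early discontinuation of study drug by OL treatment group, and the SAP 11.2.1 listing shows treatment period, treatment group and study day of discontinuation.
- SAP 11.2.1 contains no rule that places such an AE in the DB period, and the 28-day sentence may already bring it into the OL period.

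Two further points limit the size. A symptom that resolves and then recurs at Months 7 to 9 has a new start date and counts as an OL TEAE, so only symptoms that persist across Week 24 are affected. And if eCRF completion guidelines, which are not among these documents, require a new record at worsening, the problem largely goes away. Safety is also summarized descriptively, without hypothesis tests.

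All of this narrows the point without removing it. The disposition table and the listing do not correct the by-period TEAE tables, and worsening that does not stop treatment appears in neither.

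**Conclusion.** The inconsistency is real and confined to two places. First, an AE with onset in the DB period that worsens on open-label crinecerfont in a subject who continues is, as the rules stand, never an OL TEAE. Second, for a DB-onset AE that leads to stopping open-label drug, the period is undefined.

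The number affected cannot be computed from the documents. It is probably small: the 0.55 to 3.3 subjects shown above rest wholly on assumed rates and cover all worsening, with discontinuations a subset. The conclusion assumes that sites do not routinely open a new AE record when intensity or frequency increases. It does not extend to a claim that harms are lost from the report or that the DB comparison is materially distorted. Correction is still worthwhile because the OL tables are the ones a reader will use for first exposure in former placebo subjects.

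**What to change.** 1. In SAP 11.2, state that an AE ongoing at the first OL dose which afterwards increases in intensity or frequency is also an OL-period TEAE. Identify it from a new AE record at worsening where one exists, and add an eCRF completion instruction so that such a record is opened from now on.
2. In the same section, state that the 28-day sentence extends only the upper end of the window and does not admit AEs with onset before the first OL dose.
3. In SAP 11.2.1, tabulate AE discontinuations under the period and treatment in which study drug was stopped, using the recorded last-dose date.

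Items 2 and 3 need only SAP wording and dates already collected. Item 1 costs more for existing data: Protocol 11.2 asks for onset and resolution dates and intensity but no date of worsening, so some site queries may be needed. Some events will appear in both periods' tables, which a footnote should say. No new study procedures are required.
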